## **Robotic Training Group (Robotic Group): Procedure**

### ***Robotic therapy protocol description:***

The "Robotic" group will be trained using a robotic training protocol, designed to incentivize recovery of volitional motor control by dynamically changing task demands throughout the training period. One or more target tasks will be chosen to incentivize motor activity mimicking different sub-functions of gait, including some which are not normally excited in typical cycling behavior. Candidate tasks include: leg swing-through (hip flexion with knee extension near the most proximal pedal position); leg retraction (hip extension with knee flexion near the distal pedal position); leg extension (hip and knee extension – the power stroke of normal pedaling); leg retraction (hip and knee

flexion –the passive recovery stroke in normal pedaling); step-like loading (hip and knee extension while bike pedals backward through proximal pedal position, then hip and knee flexion through the distal position); and a “foot placement-like” task (alternating medial and lateral force) during normal pedaling. Also, tasks may be designed to target non-gait motions such as hip ab/adduction. The required task may be changed periodically, to incentivize attention to task and cortical control, rather than short-term adaptation (e.g. cerebellar).

A user display screen will indicate the desired task at all times, and indicate measures of asymmetry and performance. Performance will be defined as “task matching performance,” computed as the normalized projection of the vector-valued foot force or EMG signal (all channels) onto the specified task vector. Using this metric, 1.0 indicates perfect task matching; zero (0.0) indicates no force/EMG signal in the direction of the specified task; negative values indicate force production opposed to the specified task (impossible for EMG), and values greater than 1.0 indicate excess force or EMG activity in the specified pattern. We will also explore other methods for reducing multidimensional data to informative summary measures. Performance will be displayed to the user on a computer screen using a “speedometer” or similar graphical display, and will be incorporated into the control system of the robotic cycle and recorded for later analysis. Alternative measures of performance may also be used.

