The controller will reward good performance with increased crank speed, and will penalize errant coordination with decreased crank speed. The subject’s explicit goal will be to maintain a constant speed; this will only be achievable through proper motor control. Errors in either direction (too high/too low) will result in a crank speed error, representing imperfect performance. As subjects gain skill in the task, task difficulty will be increased by increasing the target signal magnitude of the specified task. This specific task is one among many possible therapy designs, which this Pilot study is intended, in part, to choose among. The specific reward structure and task definitions may be modified based on tests with healthy controls as well as early patients, in order to optimize the therapy delivered. All forms of task will involve only seated pedaling motions. Possible other tasks include (but are not limited to): pedaling that emulates a typical bike or exercise bike; tasks that change resistance torque instead of crank speed as a reward; tasks that reward forces opposing the motion of the pedals; and tasks that use a variety of different calculations to determine the “task matching performance” metric.

This therapy protocol will occupy 30 minutes of each training session. Prior to testing, EMG electrodes will be placed on the major muscles of both legs, a procedure that takes roughly 15 minutes. Another 15 minutes is allotted for changing clothes, briefing

and debriefing the subject, and other ancillary study activities. The total time allotted per training session is 1 hour.

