### **Data Processing/Data Analysis**

#### ***Behavioral Data:***

For the analysis of pre- and post- measures on the behavioral data, we will perform repeated measures ANOVA tests with time as the independent variable and score on

each behavioral test as the dependent variable.

In order to assess the overall effect of the rehabilitation protocol, we will perform multiple regression analyses to determine the extent to which data from each modality explains the proportion of the variance in the behavioral outcomes. The dependent variable is the score on the behavioral test and the predictors are the task tracking performance (error) in EMG and foot force during the last training session, and the percent signal change in targeted brain areas from the fMRI data.

In addition, we will also perform a multivariate ANOVA to examine the mixed model with Time of testing (pre, post) as a within subject factor, Group (robotic therapy, aerobic therapy) as the between-subject factor, and dependent variables of percent signal change from the fMRI data and each of the behavioral scores. This will help us to determine if there is a significant difference between the groups in terms of behavioral performance and functional activations and also to determine whether these dependent measures change over time.

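### The regression introduced as assessing the protocol's overall effect can show only association and omits the baseline score; relabel it as exploratory and add baseline (minor)

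*Combined protocol and SAP*

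**What the plan says.** All of this is in the combined protocol and SAP.

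- **The regression (Data Processing/Data Analysis, Behavioral Data).** It opens with "In order to assess the overall effect of the rehabilitation protocol" and then gives a narrower aim: how much of the variation in behavioral outcomes each source of data accounts for. On the outcome side, "The dependent variable is the score on the behavioral test". For the explanatory side, the plan states that "the predictors are the task tracking performance (error) in EMG and foot force during the last training session", plus fMRI percent signal change in the targeted areas. Group and the pre-training score are not listed. The text does not say whether the score is the post-training value or a change, or which patients enter the model.
- **The between-arm model (next paragraph).** A multivariate model with Time within subjects and Group between subjects is planned, with the comment "This will help us to determine if there is a significant difference between the groups in terms of behavioral performance".
- **Tracking performance (Robotic therapy protocol description).** It is "computed as the normalized projection of the vector-valued foot force or EMG signal (all channels) onto the specified task vector".
- **The aerobic arm (Aerobic Training Group: Procedure).** The robotic task is replaced by pedaling at a set speed and a heart-rate-based power level. No EMG or foot-force reference is named.
- **Sample Size.** 16 evaluable patients per group, 20% dropout, 20 enrolled per group. No sample size, power or R-squared figure is given for the regression.

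**The concern.** A model whose predictors all arise during or after training, and which has no term for treatment arm, does not estimate the effect of the treatment protocol. It describes which measurements go with which outcomes. A reader who takes the opening clause at face value could report variance explained as evidence that the therapy works.

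The missing baseline makes this worse. Patients who walk better at entry will tend to walk better at the end, and may also track the task better or show a different fMRI signal. Without the baseline score in the model, such a predictor gets credit for walking ability the patient already had. At stake is a secondary reading of the data, for instance which training measure to carry into the later full-scale study that the recruitment section mentions. The trial's treatment comparison is not at stake.

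**Working it through.** **1. Number of completers.** The plan's 16 reproduces from its own formula for the six-minute walk, one-tailed: 2 × ((1.65 + 0.84) × 171.1/154.3)² = 15.2, so 16. Enrolment is 16/(1 − 0.20) = 20 per arm. The regression therefore has about 16 patients if only the robotic arm enters and about 32 if both arms do.

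**2. Number of predictors.** There are two error terms (EMG, force) plus brain regions. The Secondary outcomes section names three regions. Assumption: one region at a time gives 3 predictors; all three give 5.

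**3. Baseline.** Assumptions, none from the documents: pre-post correlation r_pp of 0.8 to 0.9; predictor-baseline correlation r_b of 0.3 to 0.5; no other link between predictor and outcome; equal pre and post variance. Signs are taken as positive; reversing r_b reverses them.

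- Correlation of predictor with post score = r_b × r_pp: 0.3 × 0.8 = 0.24; 0.3 × 0.9 = 0.27; 0.5 × 0.8 = 0.40; 0.5 × 0.9 = 0.45. Squared, the extremes are 6% and 20% of variance.
- Coefficient once baseline is in the model: zero by construction. A simulation of 1,000,000 draws put it within 0.0011 of zero.
- Correlation of predictor with change = −r_b × √((1 − r_pp)/2): from −0.3 × √0.05 = −0.07 to −0.5 × √0.10 = −0.16, which is 0.4% to 2.5% of variance.
- Simulated rejection rate of a nominal 5% test of one such predictor against the post score (5,000 runs per scenario, same correlations): 14% to 43% at n = 16 and 26% to 75% at n = 32 without baseline; 4% to 5% with it.

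**4. Chance R-squared.** With no association, expected R-squared = p/(n − 1).

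| | p = 3 | p = 5 |
|---|---|---|
| n = 16 | 3/15 = 20% | 5/15 = 33% |
| n = 32 | 3/31 = 10% | 5/31 = 16% |

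Adjusted R-squared, 1 − (1 − R²)(n − 1)/(n − p − 1), removes this: at n = 16 and p = 3, 1 − 0.80 × 15/12 = 0; at p = 5, 1 − 0.667 × 15/10 = 0.

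**5. Pooling without Group.** Assume the error scale differs by 1 to 2 SD between arms, the treatment effect is 0.5 to 0.9 SD (154.3/171.1 = 0.90), error has no link to outcome, and baseline is in the model. At n = 32 the error term is then nominally significant in 16% to 71% of simulated trials, against about 5% with Group added.

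**The case against.** The strongest case against is that only one introductory clause is wrong. The same sentence states a variance-explained aim, which is an association aim and one this model can serve. The next paragraph gives the between-arm question to the Time by Group model. The regression appears in neither study objective, and this is a pilot. If only robotic patients enter, which is at least as natural a reading as pooling, a Group term is impossible and the lack of an aerobic reference is irrelevant. If the score means change, baseline accounts for at most 2.5% of variance under the assumptions used. The correlations are assumed, and an overall F-test already allows for chance R-squared.

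Most of this stands, and it limits the point to a minor one. It does not remove the mismatch between label and model, the unstated outcome and population, or the case for a baseline covariate that is already collected.

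Three stronger readings are tempting, and the documents do not support them.

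- *A reader might infer that the trial has no valid test of the therapy.* It has one, in the Time by Group model; for fMRI there are also the group comparisons in the fMRI data section.
- *A reader might infer that the regression cannot be fitted because tracking error is undefined in half the patients.* The plan does not say that the aerobic arm enters. EMG is also an outcome assessment and the aerobic protocol is otherwise the same, so signals may be recorded there; only the reference is missing.
- *A reader might infer that last-session error is not comparable between patients, so target level must be a covariate.* The text does say "task difficulty will be increased by increasing the target signal magnitude of the specified task", that "The required task may be changed periodically", and that "Errors in either direction (too high/too low) will result in a crank speed error". But no escalation rule is given, so the size of the effect cannot be worked out. Target magnitudes for different tasks need not share a scale, and the documents do not say that target level is logged. That covariate might not restore comparability, and it is not recommended here.

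**Conclusion.** The concern holds in limited form. As specified, the regression can describe how much outcome variance EMG error, force error and fMRI signal explain, but it cannot assess the overall effect its opening clause names. If the outcome is the post-training score, a predictor with no link to outcome beyond baseline could appear to explain 6% to 20% of it, conditional on the correlations assumed above. The Group term and the aerobic reference matter only if the arms are pooled. The chance figure of 20% to 33% belongs to a robotic-only model; it should not be attached to a pooled one, where it is about 10% to 16%.

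Calling every predictor a during- or after-training measure takes fMRI percent signal change as the after-versus-before quantity. The fMRI data section uses the term that way, but also for the value at each time point. No figure in the plan is shown to be wrong. Severity is minor.

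**What to change.** 1. Describe the regression as an exploratory association analysis, and take the overall effect from the Time by Group model already planned.
2. State the dependent variable as the post-training score, and add the baseline value of the same test as a covariate.
3. Name the analysis population. Keep all modalities in one model, fitted in the robotic arm, where tracking error is defined; separate tracking and fMRI models would lose the planned comparison of modalities. If a common EMG and force reference is defined for both arms and they are pooled, add a Group term.
4. Report adjusted R-squared. Giving it for baseline alone and then with the modality terms added keeps the variance-explained aim visible, since baseline by itself would explain 0.8² to 0.9², or 64% to 81%, under the assumed correlations.

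**Cost.** Wording only; no new test, visit or patient. Baseline uses one degree of freedom: at n = 16, residual degrees of freedom go from 16 − 1 − 3 = 12 to 11 with two errors and one region, or from 10 to 9 with three regions. If pooled at n = 32, baseline and Group together take 28 to 26, or 26 to 24. Restricting to the robotic arm also leaves the aerobic arm's fMRI data out of this one analysis; they remain in the group comparisons.

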5. Center of Pressure (COP): Center of pressure represents the average location of the vertical force under the feet; its motion is used as an indicator of balance control. Our protocol is a modified version of the ‘Clinical Test of Sensory Interaction and Balance’ (Rehab Measures - Clinical Test of Sensory Interaction and...). COP will be recorded during two 60-second trials of standing as motionlessly as possible on a pressure platform: one with eyes open, the other with eyes closed. During the eyes-open trial, subjects will be instructed to focus their eyes on a spot on the wall a distance in front of them. Metrics of COP control will be computed, including excursion, average velocity, standard deviation, and an estimate of center of mass location (Hof, 2005).
6. Stroke Impact Scale (SIS): The Stroke Impact Scale, or SIS, was created to assess changes in impairments, activities and participation following a stroke will be used in the pre-training and post-training phase of this study. Although the SIS form allows for proxy completion, for this study, subjects will be completing the SIS themselves.
7. Mini-Mental Status Examination (MMSE): The MMSE is a screening tool that

provides a brief, objective measure of cognitive function. We will use the original standard MMSE (Folstein, 1975).

8. Center for Epidemiologic Studies-Depression Scale - Revised (CESD-R): The CESD-R is a self-report scale and includes 20 items that survey mood, somatic complaints, interactions with others, and motor functioning.

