### **Sample Size**

Below we give sample size calculations based on the gait outcome measures (six-minute walk test (6MWT), self-selected walking speed (SSWS) and fastest comfortable walking speed (FCWS)), as well as the expected changes in brain activations:

The sample size required per group is computed using the following formula:  $N$  (per group) =  $2 * ( (z(1-\alpha/2) + z(\beta)) * \sigma / d )^2$ , where  $d$  is the expected difference in outcome value, post- vs. pre-training;  $\sigma$  is the estimated standard deviation;  $\alpha$  is the alpha error we would like to control; and  $\beta$  is the statistical power. Here we set a statistical goal of 80% power ( $\beta = 0.80$ ,  $z(\beta) = 0.84$ ) and  $\alpha$  level 0.05 ( $z(1 - \alpha/2) = 1.96$ ).

Based on a recent study of locomotor rehabilitation in chronic stroke (Bowden et al., 2013), we expect: a difference in 6MWT of 154.3 +/- 171.1 meters; a difference in SSWS of 0.21 +/- 0.13 m/s; and a difference in FCWS of 0.18 +/- 0.15 m/s. These give sample size estimates of 20, 6 and 11 subjects, respectively. This sample-size estimate is conservative, using a two-tailed test when in fact we expect to test explicitly for an

increase (one-tailed test). For a one-tailed distribution (using  $z(1 - \alpha) = 1.65$ ), sample size estimates are 16, 5 and 9 subjects.

For fMRI signal changes at the single voxel level, we expect to achieve statistical power of 80% with a significance cutoff of alpha = 0.05 using a sample size of 12 subjects, as reported in literature (Desmond and Glover, 2002).

The maximum of all sample size estimates for two-tailed tests is 20 subjects. However, the outlier is the 6MWT; without this, the maximum would be 12 subjects. Balancing the practical (budgetary, time) need for a small sample with the need to capture as many metrics as possible, **we choose a sample size of 16**. This sample size just captures the expected change in 6MWT (in a one-tailed test) and is well above the necessary sample size for other outcomes. Based on previous experience, we estimate a 20% dropout rate (due to patients not being able to complete all sessions, or not coming back for post training evaluation). We therefore propose to enroll 20 patients per group (robotic, aerobic), for a total of 40 patients.

Up to 20 healthy controls will be enrolled to form a normal data set of similar size to each patient group.

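### The only between-arm test of behavior is a MANOVA on an open-ended list of variables with 30 error degrees of freedom, so its power falls steeply with each variable added

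*Combined protocol and SAP*

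**What the plan says.** Under Data Processing/Data Analysis, Behavioral Data, three analyses are described.

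- A repeated measures ANOVA on each behavioral test, with time as its only factor.
- Multiple regressions of the behavioral scores on training performance and fMRI signal, with no Group term.
- A multivariate ANOVA with Time (pre, post) within subjects and "Group (robotic therapy, aerobic therapy) as the between-subject factor". Its outcomes are "dependent variables of percent signal change from the fMRI data and each of the behavioral scores".

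The plan does not list these outcomes, count them or reduce them to a subset. The Behavioral Assessment section names many tests, and some yield several numbers. Center of pressure, for example, is recorded in two trials and gives metrics "including excursion, average velocity, standard deviation, and an estimate of center of mass location".

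The Sample Size section works from three separate univariate gait calculations and one single-voxel fMRI figure. There "we set a statistical goal of 80% power", then "we choose a sample size of 16" per group. With dropout ("we estimate a 20% dropout rate"), the conclusion is: "We therefore propose to enroll 20 patients per group (robotic, aerobic), for a total of 40 patients". No power is given for the joint test.

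**The concern.** The primary objective is a comparison of robotic with aerobic pedaling on lower-limb function. Of the three behavioral analyses, only the MANOVA contains Group, so the comparison of arms on gait depends on it. The fMRI signal does not: the fMRI data section gives percent signal change its own two-group t-test and its own Group by Time ANOVA.

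A two-group MANOVA spends one denominator degree of freedom on every added outcome. A gait effect then has to be detected alongside cognition, mood, pain, muscle tone, balance and brain signal, most of which may not differ between arms. A non-significant joint result could come from dimension alone, and could be misread as showing that the two therapies do equally well.

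**Working it through.** **Plan's own figures.** Per group, N = 2 × ((z₁₋α/₂ + z_β) × σ/d)².

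- 6MWT (154.3, SD 171.1): 2 × (2.80 × 171.1/154.3)² = 19.3, so 20. One-tailed with 1.65: 15.2, so 16.
- SSWS (0.21, SD 0.13): 6.01 and 4.8; the plan gives 6 and 5.
- FCWS (0.18, SD 0.15): 10.9 and 8.6, so 11 and 9.
- Dropout: 16/0.8 = 20 per group.

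All agree with the plan (6.01 is rounded down). The chosen 16 is the one-tailed 6MWT figure: "This sample size just captures the expected change in 6MWT (in a one-tailed test").

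**The joint test.** With two groups and two times, the Group by Time test is Hotelling's T² on the p change scores. For n per group and N = 2n:

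- error df = N − 2 = 32 − 2 = 30;
- F = T²(N − p − 1)/(p(N − 2)) on p and N − p − 1 = 31 − p df;
- noncentrality = (n/2)D² = 8D², where D is the Mahalanobis distance between arms.

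The error matrix has rank at most 30, so the test does not exist for p > 30. If all 40 patients complete, the error df and the limit are 38.

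**How many variables.** The documents do not say, so two counts bracket it.

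- One score per test: 6MWT, TUG, SSWS, FCWS, COP, SIS, MMSE, CESD-R, leg strength, pain, Ashworth and Fugl-Meyer (12), plus three regions of interest = 15.
- Listed sub-scores: nine single scores, COP 4 × 2 trials = 8, Ashworth at each hip and knee = 4, leg strength per leg = 2, five IMU measures, and regions in both hemispheres = 6. The sum is 9 + 8 + 4 + 2 + 5 + 6 = 34. With leg strength as one score and 3 to 6 fMRI signals, it is 30 to 33. No EMG measure is counted.

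**Case A: only 6MWT differs.** d = 154.3/171.1 = 0.902, D² = 0.813, noncentrality 8 × 0.813 = 6.51. The other variables are null and uncorrelated with 6MWT; level 5%.

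| p | df | Power, 16 per arm |
|---|---|---|
| 1 | 1, 30 | 69% |
| 3 | 3, 28 | 49% |
| 15 | 15, 16 | 17% |
| 18 | 18, 13 | 13% |
| 25 | 25, 6 | 8% |
| 30 | 30, 1 | 5.5% |
| 31 or more | none | not computable |

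With 20 completers per arm, power at p = 15 is still only 24%.

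**Case B: all three gait effects differ between arms.** The standardized effects are 0.902, 1.615 and 1.200. Other variables are null and uncorrelated with gait. The gait correlation is an assumption; it is not in the documents. At correlation 0, D² = 0.813 + 2.609 + 1.440 = 4.86; at 0.5 it is 2.82; at 0.8 it is 3.06. At p = 15 and 16 per arm, power is 85%, 57% and 61%. It dips to 55% at correlations near 0.6.

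**Case C: half of each effect in B.** D² is a quarter of the above: 1.22, 0.70 and 0.76. Power at p = 15 is 24%, 15% and 16%, with a low of 14% near 0.6. With only the three gait variables in the test it is 68%, 43% and 47%.

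**The case against.** Two stronger readings are tempting.

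A reader might infer that the MANOVA cannot be run. The documents do not establish that. The same section speaks of the score on each behavioral test, and one score per test gives about 15 variables, which is computable. Passing 30 requires entering sub-scores. The IMU measures sit under a separate Gait Assessment heading, and without those five the count of 34 falls to 29. Even 34 is computable with 36 completers (36 − 2 = 34). What stands is that the list is open, and that a literal use of the listed metrics reaches or passes the limit at 32 completers.

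A reader might also infer that a null result is nearly certain. Case B shows otherwise at 15 variables. The Sample Size section, however, defines these effects as post- versus pre-training differences, and the comparator is itself an active pedaling program, so they are optimistic as differences between arms. The same caution applies to the 0.90 SD in Case A.

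It can fairly be said that the harm arises largely because the univariate behavioral ANOVA omits Group. With Group there, this MANOVA would be supplementary in a pilot study. As written, it is the only between-arm behavioral test.

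Missing items are a further uncertainty. A standard MANOVA uses complete cases, which would lower the error df below 30 if completers lack a score or scan, but the documents state no missing-data rule.

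**Conclusion.** The concern holds in this form: the only described comparison of the arms on behavior is a joint test whose variables are unspecified, and at 32 completers each added variable costs substantial power. At about 15 variables the test runs. Its power is 17% if only 6MWT differs by 0.90 SD, 15–24% at half the three planned gait effects, and 57–85% if all three are taken in full as between-arm differences (gait correlations 0, 0.5 and 0.8). At roughly 30–34 variables it is at or past its limit and may not be computable.

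These figures assume 16 complete cases per arm, a two-sided 5% level, the Sample Size SDs applied to change scores, and non-gait variables that are null and uncorrelated with gait. The documents support neither a claim that the test is bound to fail nor one that it is adequately powered.

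**What to change.** In the Behavioral Data section, replace the all-variable MANOVA with a joint test of Group on change in 6MWT, SSWS and FCWS, the three measures used for sizing. In Case A this raises power from 17% to 49%; in Case C, from 15–24% to 43–68%. Analyse each remaining behavioral score in its own Group by Time model, and list those scores, stating which sub-scores count. Percent signal change keeps the two-arm analyses already in the fMRI data section.

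This changes wording only; no visit, measurement or patient is affected. The cost is more separate tests: at one score per test, 12 − 3 = 9 outside the gait set, and more if sub-scores are analysed. These should be labelled exploratory or adjusted for multiplicity. The single omnibus test across behavior and brain signal is given up.

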## **Study Objectives**

### ***Primary objective***

To examine the effect of a robotic pedaling therapy program that rewards coordinated foot pedal forces and EMG patterns on lower-limb function during pedaling and walking, in comparison to an aerobic pedaling task.

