***fMRI data:***

SPM5 (Wellcome Department of Cognitive Neurology, London, UK) will be employed for motion correction and used to normalize the EPI BOLD images to a standard space using a 12 parameter linear transformation. The images will be then spatially smoothed using an 8.0 mm Gaussian kernel. Finally, the statistical package contained within SPM5 will be used to estimate the effects of condition at each voxel according to the general linear model. The analysis will be entered into SPM5 as an epoch design of the fixed response/box car form convolved with canonical HRF, reflecting the appropriate activation and rest periods within the total scanning period. Images will be high-pass filtered at 128 s to remove low- frequency drifts in blood oxygen level-dependent signal.

Percent signal change (after vs. before) will be compared statistically between the two groups using unpaired two-sample t-tests between the robotic and aerobic groups. A repeated measures ANOVA will be performed with the dependent variable being the percent signal change and between subjects factor Group (robotic therapy, aerobic therapy), and within subject factor Time (before and after training).

Along with percent signal change over time, we will also compute region-wise laterality index. ROIs will be predefined in each hemisphere. For each ROI, laterality index (LI) will be defined as: Number of activated voxels in the affected hemisphere / [voxels in the left hemisphere + voxels in the right], thus giving LI for each ROI. LI = 0.5 indicates symmetrical activation; LI < 0.5 indicates an activation deficit on the affected side, and LI > 0.5 indicates increased activation of the affected side. This index will provide a way of

understanding the contribution of each brain area (ROI) to the overall task-related activation in one session and changes in laterality over time. The percent signal change and LI are purely quantitative measures, in order to ensure that change in plasticity over time is captured adequately and does not rely on individual fMRI reader's abilities to gauge these changes simply on the basis of a "visual read" of the fMRI scans.

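### For the gait outcomes, the only between-arm model is read as a group difference and a change over time; Group x Time is never named as the robotic-versus-aerobic test

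*Combined protocol and SAP*

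**What the plan says.** The Primary objective is comparative: the effect of robotic therapy "on lower-limb function during pedaling and walking, in comparison to an aerobic pedaling task". The primary outcome section lists 6MWT, SSWS and FCWS.

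Data Processing/Data Analysis, under Behavioral Data, plans three analyses of these scores:

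1. A repeated measures ANOVA in which time is the only independent variable, with the score on "each behavioral test as the dependent variable".
2. A multiple regression of the behavioral score on tracking error and fMRI signal, with no group term.
3. A multivariate mixed model with time of testing as the within-subject factor and "Group (robotic therapy, aerobic therapy) as the between-subject factor".

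Only the third involves the arms. Its purpose is given as follows: "This will help us to determine if there is a significant difference between the groups in terms of behavioral performance and functional activations". The same sentence adds a second purpose, which is to see if the scores move from the first testing to the last.

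The fMRI data section is different. It also plans a repeated measures ANOVA with "between subjects factor Group (robotic therapy, aerobic therapy), and within subject factor Time (before and after training", but first states: "Percent signal change (after vs. before) will be compared statistically between the two groups using unpaired two-sample t-tests".

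No section of the document names the Group x Time interaction.

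**The concern.** With two randomized arms measured before and after training, the effect of robotic over aerobic therapy is the between-arm difference in change. In the mixed model that is the interaction. The two readings that the plan gives are different quantities.

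- **Group.** A difference between the groups, taken as the Group main effect, compares each arm's average of its pre- and post-training scores. The arms are equal at baseline in expectation, so half of that average carries no treatment effect, and the stable differences between patients remain in the error.
- **Time.** A change over time, taken as the Time main effect, pools both arms. It can be present when the two therapies work equally well, so it cannot answer the comparative objective.

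Three terms are available and none is named as decisive. An analyst could report a null Group effect as no difference between therapies and still be following the text, although the interaction might show one. This affects the only planned between-arm analysis of the primary outcomes.

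**Working it through.** **Inputs.** From Sample Size: 16 evaluable patients per arm, alpha 0.05, 80% power, and differences (SD) of 154.3 (171.1) m for 6MWT, 0.21 (0.13) m/s for SSWS and 0.18 (0.15) m/s for FCWS. Not in the documents: the pre-post correlation rho, varied here from 0 to 0.9.

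**The plan's own figures.** With N per group = 2 × ((z(1−alpha/2) + z(power)) × SD / d)²:

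- 6MWT: 2 × (2.80 × 171.1/154.3)² = 19.3, plan 20.
- SSWS: 2 × (2.80 × 0.13/0.21)² = 6.01, plan 6.
- FCWS: 2 × (2.80 × 0.15/0.18)² = 10.9, plan 11.
- One-tailed, with 1.65 + 0.84 = 2.49: 15.2, 4.8 and 8.6, plan 16, 5 and 9.
- Dropout: 16/(1 − 0.20) = 20 per group.

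The figures reproduce, apart from a trivial rounding of 6.01 to 6.

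**The two terms.** Let delta be the treatment effect on the post-training score, s the SD at each time and n the number per arm.

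- Interaction: effect delta, per-patient variance of change 2s²(1 − rho).
- Group main effect: effect delta/2, per-patient variance of the pre/post average s²(1 + rho)/2.

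Each noncentrality is effect / (SD × sqrt(2/n)). The ratio of main effect to interaction is therefore

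(1/2) × sqrt(2(1 − rho)) / sqrt((1 + rho)/2) = sqrt((1 − rho)/(1 + rho)).

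**Power when the interaction has 80%.** With n = 16 (30 df) and two-sided 0.05, 80% power needs a noncentrality of 2.895. Multiplying by the ratio and using the noncentral t distribution:

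| Assumed rho | Ratio | Noncentrality, Group | Power, Group main effect |
|---|---|---|---|
| 0 | 1.00 | 2.90 | 80% |
| 0.3 | 0.73 | 2.13 | 54% |
| 0.5 | 0.58 | 1.67 | 37% |
| 0.7 | 0.42 | 1.22 | 22% |
| 0.8 | 0.33 | 0.97 | 15% |
| 0.9 | 0.23 | 0.66 | 10% |

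Half of the power (80% to 40%) is lost at rho of about 0.46.

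**Power with the plan's own effects.** This reads the stated SD as the SD of change, with n = 16, two-sided:

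| Outcome | Interaction | Group, rho 0.5 | Group, rho 0.8 |
|---|---|---|---|
| 6MWT | 69.4% | 29.7% | 13.1% |
| SSWS | 99.3% | 72.3% | 31.4% |
| FCWS | 90.7% | 47.5% | 19.5% |

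A simulation for 6MWT (20,000 trials) agrees: 70% against 30% at rho 0.5, and 70% against 13% at rho 0.8.

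The absolute powers in this second table are optimistic. The plan's d "is the expected difference in outcome value, post- vs. pre-training", yet it enters a two-group formula, so the table treats the whole pre-to-post change as the difference between arms. The ratio of the two terms is unaffected.

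**The case against.** **The plan never says main effect.** A mixed model with these two factors ordinarily includes the interaction, the sentence on its purpose is loosely worded, and a difference between the groups could be meant as a difference in change. Elsewhere the plan thinks in terms of change: patients act as their own controls (Research Design and Methods), and the secondary imaging outcomes are defined as changes. This stands in part. The model can give the right term, so the defect lies in the stated reading. But expecting an analyst to look at the interaction is not prespecification, and no wording for the gait scores points there.

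**A reader might infer that the fMRI analysis has the same gap.** The document does not support that for percent signal change. With two arms and two times, an unpaired t-test on change is the Group x Time test. The planned t-test does this already, provided that after versus before means change across training.

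**A reader might infer that most of the power is necessarily lost.** That is conditional. Nothing is lost at rho 0, and SSWS keeps 72% at rho 0.5. If the stated SD is cross-sectional, SSWS keeps about 67% at rho 0.8 (normal approximation). The calculations are also univariate, whereas the plan describes a multivariate model.

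**A reader might infer that the plan would count a Time effect as success for robotic therapy.** It does not say so; it uses Time to ask whether scores change, which Time answers. If both arms gained an assumed 0.3 SD at rho 0.8, Time would be significant in about 74% of trials. That would be correct detection of change, not a false finding between arms.

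**This is a pilot.** True, but the primary objective is still a comparison of arms.

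**Conclusion.** The point holds for the behavioral scores, which include every primary gait outcome. The one planned between-arm analysis is described through a group difference and a change over time, and neither, as worded, is the robotic-versus-aerobic effect. That the Group main effect estimates half the treatment effect does not depend on the correlation; it follows from equal expected baselines under randomization.

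The power cost does depend on the correlation. Against 80% for the interaction it runs from no loss at rho 0 to a fall to 10% at rho 0.9, assuming equal variances at the two times, 16 per arm and a two-sided 0.05 test of one outcome at a time. The documents do not support a claim that the model cannot test the objective, that the loss is large whatever the correlation, or that the percent signal change analysis lacks the right test.

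**What to change.** Under Behavioral Data, replace the sentence on what the mixed model will determine with text such as:

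*For each gait outcome (6MWT, SSWS, FCWS), the effect of robotic versus aerobic therapy is the Group x Time interaction, that is, the between-arm difference in pre-to-post change, reported with a 95% CI. The main effects of Group and Time will not be interpreted as evidence of a difference between therapies.*

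The fMRI data section needs at most a consistency note that its t-test on after-versus-before percent signal change and the Group x Time term of its ANOVA are the same test.

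The cost is two sentences in one section. The model, the data collected and the sample size stay as they are.
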